### 1.2 Rationale

Lack of self-efficacy, attributed to poor understanding of the disease and uncertainty regarding the importance of exercise, has been shown to be a major barrier to exercise uptake in patients with PAD and IC. Educating patients with IC about their disease pathology and the benefits of walking is key to enhancing success of secondary prevention strategies for people with IC. We recently piloted a structured, patient-centred education intervention (SEDRIC) with the specific aim of educating patients with IC about their condition, improving patient ownership, and promoting self-managed walking. In addition to improved treadmill walking distances, we found out that there was a trend for patients to increase their daily PA.

For patients with IC to gain benefits of secondary prevention, exercising beyond the point when pain occurs is recommended, representing another barrier to engagement in PA. Despite this, our systematic review found that pain management as a route to facilitate exercise and PA has rarely been explored. Recent interest has focused on the use of TENS (a low-cost, non-invasive pain management device) to improve angiogenesis, muscle function, pain and walking distances in patients with IC. TENS has a strong placebo effect in pain conditions, and testing effectiveness against placebo is advocated. In a proof-of-concept pilot study, we demonstrated that TENS could significantly improve pain and increase treadmill walking distances above placebo levels. Our exploratory study also established that home use of TENS was both acceptable and provided self-reported improvement in PA in individuals with IC.

Although patient-centred education (SEDRIC) and TENS have both demonstrated potential to improve daily PA in people with IC, the use of these components in combination has not previously been evaluated. We therefore propose a 2 x 2 (TENS versus placebo TENS x SEDRIC versus no additional education) feasibility RCT that will compare use of TENS against placebo TENS with and without a patient-centred education programme.

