## 4 Trial procedures

**Study design:** This is a double-blind, feasibility RCT. TENS/placebo and patient education interventions will be 6 weeks in duration and all participants will receive secondary prevention therapy as recommended by NICE including advice to exercise (usual care). A sub-group of participants (those recruited within the first 8 months of recruitment) will be followed up for 3 months post-intervention. A qualitative, focus group study will also be conducted after final follow up.

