### Visit 2- Second Assessment Visit (usually within 2 weeks after visit 1):

Participants will then attend for a second visit to undergo a second Treadmill test, and to return the activPAL and sleep diary. Only participants with ≤20% variation in ACD will continue in the trial. After this visit eligible participants will be randomized, and given a date for them to return for intervention (TENS/Placebo ± Education) as applicable. Recruitment and randomisation will be done in waves to allow groups to be formed for the education session.

Second Assessment Visit (30 mins)	Time (mins)	Responsible
Return of ActivPAL by participants	5	RN/UA
Treadmill protocol • McGill Pain Questionnaire (5 minutes after completion of the treadmill protocol)	20	

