The superiority comparison will be implemented to compare change in physical activity and PROMs between treatment groups (PE+TENS, PE+Placebo TENS, TENS) versus Placebo TENS. Also superiority comparison will be implemented for within treatment groups from baseline. A non-superiority comparison shall be made between the PE+TENS group versus each of the PE+Placebo TENS, TENS groups. The feasibility, acceptability (the recruitment, retention, outcome completion, intervention uptake and attrition rates, and patient tens feedback) and adverse events data will be summarised by randomised group and overall using descriptive statistics. No formal statistical tests comparing the randomised groups will be pre-specified. Framework analysis will be implemented for the qualitative focus group data.

Statistical analysis and stopping guidance

Interim analysis will not be conducted, and the study will stop at last patient last study visit. All outcomes will be analysed collectively at the end of the study. P-value will be set at $p < 0.05$.

Timing of outcome assessments

Physical activity and PROMs outcomes will be assessed at baseline, end of six weeks intervention (up to 2 weeks window), and 3 months post-randomisation (up to 2 weeks window). The recruitment, retention, outcome completion, intervention uptake and attrition rates will be assessed at the end of the study. Blinding and patients acceptability of TENS and

ease of use will be assessed at the point of patient exit from the study. Further assessment regarding patients' qualitative experience of intervention will be done at 3 months post-randomisation (up to 2 weeks window).

SECTION 4: STATISTICAL PRINCIPLES

Level of confidence interval and p-values

Analysis will be conducted at 95% CI, and 0.05 level of significance.

Adherence and Protocol Deviations:

Patient adherence to the intervention will be defined, as applicable, by patients attendance at the education session, and answering to at least one of the 2-weekly phone calls, and/or using TENS at least 30 mins per day 3x/wkly for at least 50% of the 6 weeks of intervention. Specifically, the TENS log (questionnaire) as well as inbuilt record of TENS device usage will both be used to analyse patients utilisation of TENS. Researcher adherence to intervention protocol will be defined as implementation of intervention and outcome assessment according to the approved study protocol.

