To determine the feasibility of conducting a definitive trial, descriptive statistics will be used to report the number and proportion of participants who meet the inclusion criteria, who consented to participating, and who dropped out during the trial. Also descriptive analysis will report compliance with intervention by recording participants' attendance to education session, follow up calls, attendance to TENS training session, (rate of use of TENS) rate of outcome measure completion, and total accelerometer wear time. Specifically, the TENS log (questionnaire) as well as inbuilt record of TENS device usage will both be used to analyse patients utilisation of TENS. Acceptability of TENS will be obtained by TENS feedback questionnaire

Further exploration will be carried out to determine factors that impact on propensity to participate looking at the difference in characteristics between participants and non-participants. If less than 10% of the individuals with PAD/IC in the clinic are eligible to participate, or if less than 10% of eligible patients agreed to participate, then the eligibility criteria and recruitment strategy will be adjusted prior to conducting a definitive trial. Adjustment of the recruitment strategy in a definitive trial will be made comparing the difference in the baseline characteristics between participants and non-participants. Similarly, association between participants' baseline characteristics and trial outcome will also inform decision on adjustment of recruitment strategy and stratification factors in the definitive trial. Data collection for the definitive trial will be adjusted based on the information related to type, quantity of missing data, and the mechanisms by which these data are missing.

The transcripts from the focus group discussions will be analysed using framework analysis. The data gathered from the exit interview will form part of acceptability analysis and be used to adapt the intervention to enhance its acceptability in a definitive trial.

Primary efficacy analysis

Differences in the change in ACD will be analysed and effect scores calculated using Chi-squared tests, Mann-Whitney U or Wilcoxon signed-rank tests as applicable for between and within-group comparisons and log-rank method for pooled samples or sub-strata. Baseline participants' variability will be controlled for using the analysis of co-variance.

Secondary efficacy analysis

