Recruitment target/Number recruited.					
Recruitment rate (n/centre/month)					
Outcome completion rate					
Reasons for withdrawal from intervention					
Retention rate (proportion of participants with valid primary outcome data at 3-months follow-up)					
Retention rate (proportion of participants with valid ActivPAL outcome data at 3-months follow-up)					
Reason for withdrawal from follow up					
Timing of withdrawal					
Intervention uptake and Adherence rate					
Attendance to PE					
Summary from phone calls					
TENS log summary					
Objective record of TENS use					
Acceptability of intervention					
Acceptability questionnaire					
Adverse events rate					
List them					
TENS blinding					

PrEPAID Statistical Analysis Plan (Version 1.0)
 Approval date:

Table 3: Changes in groups' outcomes at 6-wweks compared to placebo (usual care alone)

	TENS	PE+TENS	PE
ACD	$x \pm sd$ vs $x \pm sd$; $p=xxx(95\%cl)$		
ICD			
Daily steps			
Upright events			
Walking events			
EBCD			
ICQ			
SF-36			
7-day Average pain intensity			
Pain quality			
IPQ			
GDS-SF			
PSEQ			

*Also compare between PE+TENS and each of TENSs and PE alone (May not present in a table)

PrEPAID Statistical Analysis Plan (Version 1.0)
 Approval date:

Table 4: Changes in groups' outcomes at 3 months compared to placebo (usual care alone)

	TENS	PE+TENS	PE
ACD	$x \pm sd$ vs $x \pm sd$; $p=xxx(95\%cl)$		
ICD			
Daily steps			
Upright events			
Walking events			
EBCD			
ICQ			
SF-36			
7-day Average pain intensity			
Pain quality			
IPQ			
GDS-SF			
PSEQ			

*Also compare between PE+TENS and each of TENSs and PE alone ((May not present in a table)

Table 5: Within group comparisons between baseline and after 6 weeks intervention and 3 months follow up

	TENS	PE+TENS	PE	Usual care alone
ACD Post 6 wks Post 3 months follow up	$x \pm sd$ vs $x \pm sd$; $p = xxx$ (95%cl)			
ICD Post 6 wks Post 3 months follow up				
Daily steps Post 6 wks Post 3 months follow up				
Upright events Post 6 wks Post 3 months follow up				
Walking events Post 6 wks Post 3 months follow up				
EBCD Post 6 wks Post 3 months follow up				
ICQ Post 6 wks Post 3 months follow up				
SF-36 Post 6 wks Post 3 months follow up				
7-day mean pain intensity Post 6 wks Post 3 months follow up				
Pain quality				

PrEPAID Statistical Analysis Plan (Version 1.0)
Approval date:

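### The SAP plans superiority tests of arms against their own baseline; these have no concurrent control, cannot show an intervention effect, and should be descriptive only

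*SAP*

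**What the plan says.** SAP Section 3, Framework, plans two kinds of superiority comparison. One is randomised: "The superiority comparison will be implemented to compare change in physical activity and PROMs between treatment groups", with PE+TENS, PE+Placebo TENS and TENS each set against Placebo TENS. The next sentence adds the other: "Also superiority comparison will be implemented for within treatment groups from baseline".

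The primary efficacy analysis in SAP Section 6 names "Mann-Whitney U or Wilcoxon signed-rank tests as applicable for between and within-group comparisons" and says effect scores will be calculated. The secondary efficacy analysis does the same, and protocol 8.3 and 8.4 match both. SAP Section 4 sets the threshold: "Analysis will be conducted at 95% CI, and 0.05 level of significance". No multiplicity adjustment is stated.

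Table 5 is titled "Within group comparisons between baseline and after 6 weeks intervention and 3 months follow up". Its template cell holds two means with SDs, a p-value and a 95% CI. Its four columns include one headed usual care alone, which in this design is the Placebo TENS arm. Nothing in either document marks these results as descriptive.

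On other causes of change, protocol 1.2 and the SAP introduction say "TENS has a strong placebo effect in pain conditions". Protocol section 4 gives all participants NICE-recommended secondary prevention, including exercise advice, as usual care. The treadmill test is done at visits 1, 2 and 4 and, for some participants, visit 5. At visit 2 a stability rule applies: "Only participants with ≤20% variation in ACD will continue in the trial".

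**The concern.** A comparison with baseline asks whether an arm changed. It does not ask whether the intervention changed it. Placebo response, usual care and familiarity with the test can act in every arm, and a pre-post test credits all of them to the arm's label. The randomised placebo control is there to remove this error, and the documents themselves argue for testing TENS against placebo.

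The risk of misreading is practical. The synopsis rationale counts improvement in patient outcomes among the weightiest grounds for judging whether a definitive trial is feasible, and does not say improvement relative to control. Protocol 1.3 already supports the education programme with changes from baseline in 14 patients (30% in walking distance, 32% in quality of life). A table of within-arm p-values, planned under the word superiority, could be used in the same way.

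**Working it through.** **The plan's own figure.** Protocol 8.7 gives 16 per group for a 1.0 SD difference, 80% power, two-sided 5%. With n = 2(z₀.₉₇₅ + z₀.₈₀)²/d², this is 2 × (1.960 + 0.842)² / 1.0² = 15.70, rounded up to 16. For 20% attrition, 16/0.8 = 20 per arm, and 4 × 20 = 80. The figure is reproduced. It concerns active TENS against placebo; neither document gives power for a within-arm test.

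**Number of within-arm tests.** Table 5 has 13 outcomes × 2 times × 4 arms = 104. If the Framework sentence means only the three arms it sets against Placebo TENS, the count is 13 × 2 × 3 = 78. If nothing changed at all, 104 × 0.05 = 5.2 would be expected below 0.05 (78 × 0.05 = 3.9). Half of these, 2.6 of 5.2, would be in the direction of improvement.

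**Rejection rate with zero intervention effect.** Let every arm share a mean change of δ, in SDs of the change score. The documents give neither δ nor that SD, so δ is an assumption shown as a range. The paired t statistic then follows a noncentral t distribution with n − 1 degrees of freedom and noncentrality δ√n, and the rejection rate is P(|t| > t₀.₉₇₅,ₙ₋₁). Example: n = 16 and δ = 0.5 give noncentrality 0.5 × 4 = 2.0 and critical value 2.131, hence 46.5%.

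| Shared shift δ (assumed) | Within arm, n = 16 | Within arm, n = 20 | Between arms, n = 16 each (simulated) |
|---|---|---|---|
| 0 | 5% | 5% | 4.9% |
| 0.2 | 11.6% | 13.6% | 4.9% |
| 0.3 | 20.3% | 24.7% | 5.0% |
| 0.5 | 46.5% | 56.5% | 5.1% |
| 0.8 | 84.8% | 92.4% | 5.0% |

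The between-arm column comes from 20,000 simulated trials per row. It stays near 5% because the shared shift cancels: δ − δ = 0.

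**Check with the named test.** The plan names the signed-rank test. Simulated at n = 16 (2,000 runs), it rejects in 19.8%, 42.9% and 81.3% of arms at δ = 0.3, 0.5 and 0.8, slightly below the t-test.

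**Three months.** Only participants recruited in the first eight months are followed to this visit, so n is smaller, and it is not stated. With n = 10 (assumed) and δ = 0.5, noncentrality is 0.5 × √10 = 1.58 and the critical value is 2.262, giving 29.3%.

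**Two identical arms.** At δ = 0.5 and n = 16, exactly one of two arms with the same true change is significant in 2 × 0.465 × 0.535 = 49.8% of trials. Significance in one arm and not in another therefore says little about a difference between them.

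**The case against.** The valid analysis is already planned. The between-arm comparison comes first in the Framework, Tables 3 and 4 report it at both times, analysis of covariance is named for ACD, and the SAP says that clinical differences are not the primary purpose. All of this stands, and it limits the point to the within-arm tests.

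Several stronger readings are tempting, and the documents do not support them:

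- A reader might infer that arms will be compared by which of them reach p<0.05, or that effect sizes for the definitive trial will come from within-arm change. Neither is stated.
- A reader might infer that Placebo TENS would be declared superior to its own baseline. Table 5 includes that arm, but its title speaks of comparisons, and the Framework sentence may cover only three arms.
- A reader might take the 20% rule at visit 2 as proof of upward drift. It has no stated direction and covers ACD only. With the second baseline test, it is better seen as a partial safeguard against practice effects. It does not remove them, and it does nothing about placebo response or exercise advice.
- A reader might add seasonal change in activity. The documents do not mention season, and the point does not need it.
- The placebo effect is stated for pain conditions, not for all 13 outcomes. Exercise advice is continuing usual care and is not shown to be new after baseline.

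It is also fair to say that a 95% CI for change carries the same information as its p-value. Removing p-values alone would therefore do little; the explanatory footnote and the rule on where conclusions come from do most of the work.

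**Conclusion.** The point holds for the within-arm tests. They are planned as superiority comparisons, listed as efficacy analyses and given p-values, yet they cannot separate an intervention effect from change common to all arms. That follows from the absence of a concurrent control and needs no assumption about size.

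The size does depend on an assumption. At six weeks, with no intervention effect and a shared shift of 0.2 to 0.8 SD of change, 12% to 85% of arms would be significant at n = 16 and 14% to 92% at n = 20. At three months the rates depend on a subgroup size that is not given. Placebo response and exercise advice are documented; treadmill practice is a plausible inference.

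This does not invalidate the trial's efficacy comparison or its sample size. It is a moderate point: the change should be made, but the main comparison stands without it.

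**What to change.** 1. Delete the within-group superiority sentence from the Framework in SAP Section 3.
2. Remove the within-group tests from protocol 8.3 and 8.4 and from the primary and secondary efficacy analyses in SAP Section 6.
3. Make Table 5 descriptive: n, mean change, SD and 95% CI per arm and time, without p-values. Showing n matters most at three months. Add a footnote that change from baseline is not an intervention effect.
4. State that conclusions on potential effect, and effect sizes for the definitive trial, come only from the randomised, baseline-adjusted between-arm contrasts. Analysis of covariance is now named only for ACD, so the adjustment for secondary outcomes needs to be written in.

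Cost: a SAP revision and, because protocol section 13 requires an amendment for any protocol change, an amendment covering 8.3 and 8.4. Fewer nominally significant results will be reported. Conduct, data collection and sample size do not change, and the within-arm means and SDs remain available for planning.

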### Interventions:

**TENS:** Participants will be given TENS at intervention visit. They will be instructed to use the device daily at home or elsewhere. They will be specifically advised to use the device prior to, or during, a challenging walk each day. Challenging walk could be for activities of daily living (ADL) or planned exercise. For those with bilateral claudication they are advised to wear the device on the worst limb and could alternate it as symptoms fluctuates. The active group will receive High Frequency-TENS (120 Hz, 200µs and a patient-determined intensity of “strong but comfortable”).

**Placebo TENS:** Participants will receive the same model and instructions for use as those in the active group except that the stimulation dose is be safely altered to produce non-therapeutic, ineffective stimulation. For the purposes of blinding, participants will be told that different dosages of TENS are being tested some of which they might not feel anything even though the device is working. This method of effecting placebo has been successfully used in previous TENS trials.

Both the statistician conducting the randomization and the outcome assessor would be blinded to active TENS and placebo TENS. Importantly, participants will receive the same set of instructions as those in active TENS with the addition of a statement that two TENS are being tested. Blinding will be assessed at the end of the intervention period. Participants will be asked if they believed their TENS unit was functioning properly.

**Patient-Centred Education:** Intervention in these groups will be adopted from the successfully piloted SEDRIC study: A one-off three-hour workshop of structured group education (4-5 persons in each group) and three 2-weekly phone calls. Two educators will implement the session. Training for educators will involve completion of the DESMOND core training, reading and demonstrating understanding of the SEDRIC curriculum, and completion of at least two practice workshops that are

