Measure participant's retention throughout the trial and reasons for withdrawal
Monitor, record, manage and follow-up defined adverse events in all groups
Measure uptake of intervention (log of TENS use and attendance at education) and acceptability of these interventions via a questionnaire
Measure blinding fidelity via TENS feedback questionnaire
Outcome completion rate – number of day activPAL is worn at each outcome time point.

Efficacy outcomes

Measurement will be obtained at baseline, following six weeks intervention and at 3 months follow up

Primary efficacy outcomes

Treadmill assessed Absolute Claudication Distance (ACD) (cm).

Secondary efficacy outcomes will include:

Physical activity capacity secondary outcomes

Treadmill assessed Initial Claudication Distance (ICD), assessed by a treadmill exercise using the Gardner treadmill protocol.¹⁹ Measurement will be obtained at baseline, following six weeks intervention and at 3 months follow.

Daily physical activity. We shall specify 3 days activPAL data at each measure as minimum for including patient activPAL data in the efficacy analysis. However, activPAL were time (number of day worn) will be also be reported as part of the feasibility analysis. For secondary efficacy analysis, activPAL data outcomes: total number of **i**) steps; **ii**) upright events; **iii**) walking events; **iv**) Event-based claudication index (ratio of walking events to upright events) participants undertake in a day.²⁰

PROM secondary outcomes

Disease specific quality of life will be as assessed using the Intermittent Claudication Questionnaire (ICQ).

Generic quality of life via the SF-36;

Pain quality will be recorded using the McGill Pain Questionnaire (MPQ) 5 minutes after every treadmill test.

Average Pain intensity in the past 7 days will be recorded using a Visual Analogue Scale

Illness beliefs and psychosocial determinants of health and behaviour will be recorded using the Illness Perception Questionnaire (IPQ), Geriatric Depression Scale (Short Form) (GDS-SF) and the Pain Self-Efficacy Questionnaire (PSEQ).

Qualitative Experience outcome

Analysis Methods

Feasibility and qualitative data analysis

Descriptive statistics will be used to characterize the groups at baseline and to present the feasibility outcomes.

Outcomes related to experience and perception via focus groups will be analysed by framework analysis.

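### The Protocol times the blinding assessment at the end of treatment and the SAP times it at study exit, so the single blinding row of SAP Table 2 could mix answers given up to about 18 weeks apart

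*SAP*

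**What the plan says.** **Timing in the Protocol** (section 4, Interventions, Placebo TENS): "Blinding will be assessed at the end of the intervention period". The question follows: "Participants will be asked if they believed their TENS unit was functioning properly". No form is named.

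**Timing in the SAP** (Section 3, Timing of outcome assessments): the sentence opens "Blinding and patients acceptability of TENS and" and goes on "ease of use will be assessed at the point of patient exit from the study".

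**Instrument** (SAP Section 6, Feasibility and acceptability outcomes): "Measure blinding fidelity via TENS feedback questionnaire".

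**Visit tables** (Protocol Study Schedule and section 4.1, Visits 4, 5 and 6): the TENS feedback questionnaire appears at each of these visits, each time on condition that the participant is leaving at that visit. In the Visit 4 table the adverse-event questionnaire next to it has no such condition. No other blinding item is listed at Visit 4.

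**Who leaves when**: "A sub-group of participants (those recruited within the first 8 months of recruitment) will be followed up for 3 months post-intervention". All participants are invited to the Visit 6 focus group (Protocol section 4.1, Visit 6).

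**Reporting**: SAP Table 2 has one row, "TENS blinding", with no time point, whereas the retention rows of the same table state theirs. The SAP (Section 3, Framework) has "patient tens feedback) and adverse events data will be summarised by randomised group and overall using descriptive statistics", with no split by exit visit.

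**The concern.** The two documents give different times for the same assessment. They coincide only for participants who leave at Visit 4. For anyone who continues, the SAP and the visit tables move the blinding answer to Visit 5 or Visit 6, so its timing depends on recruitment date and on focus-group attendance.

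Blinding fidelity matters in this trial. The SAP lists it as a feasibility outcome, and both documents say that TENS has a strong placebo effect. Whether participants stayed blind during treatment is something the definitive trial needs to know. A belief reported as treatment ends and a belief recalled months later, possibly after a group discussion of the programme at Visit 6, do not measure quite the same thing. One pooled row would hide the difference.

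The exit condition is also hard to apply. Everyone is invited to Visit 6, but the number of focus groups is set by data saturation, so staff at Visit 4 or 5 may not know whether a participant is leaving. Someone expected at a later visit who does not attend has no completion of the form listed in the tables.

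**Working it through.** The plan states no figure for the lag between treatment and the blinding answer, so there is none to reproduce. The lag follows from the visit timings.

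**Inputs**
- Treatment lasts 6 weeks; Visit 4 is at its end (Protocol section 4.1). The SAP (Section 3) allows a window of up to 2 weeks and does not say whether it is one- or two-sided.
- Visit 5 is 3 months after the intervention, plus or minus 2 weeks (Protocol section 4.1, Visit 5).
- Visit 6 is usually 1 to 3 weeks after the final follow-up (Protocol section 4.1, Visit 6).
- Conversion: 3 months = 3 × (365.25 / 12) / 7 = 13.04 weeks.

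**Weeks from the end of treatment to the answer, on the Protocol's timing**

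| Exit visit | Calculation | Weeks |
|---|---|---|
| Visit 4, one-sided window | 0 to 0 + 2 | 0 to 2 |
| Visit 4, two-sided window | 0 − 2 to 0 + 2 | −2 to 2 |
| Visit 6 with no Visit 5 (one-sided Visit 4 window) | 0 + 1 to 2 + 3 | 1 to 5 |
| Visit 5 | 13.04 − 2 to 13.04 + 2 | 11.0 to 15.0 |
| Visit 6 after Visit 5 | 11.04 + 1 to 15.04 + 3 | 12.0 to 18.0 |

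**Spread within the one Table 2 row**
- One-sided Visit 4 window: 18.04 − 0 = about 18 weeks.
- Two-sided Visit 4 window: 18.04 − (−2) = about 20 weeks.

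Because the Visit 6 interval is only the usual one, 18 weeks is not a strict upper limit.

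**Sensitivity to the SAP's timing.** The SAP (Section 3, Timing of outcome assessments) counts the later assessment, including the qualitative one, as 3 months from randomisation. Visit 3 falls 0 to 3 weeks after randomisation (Protocol section 4.1). The lag after treatment is then 13.04 − 6 − 3 = 4.0 to 13.04 − 6 − 0 = 7.0 weeks. With the 2-week window this becomes 4.0 to 9.0 (one-sided) or 2.0 to 9.0 (two-sided). The spread is 9.04 − 0 = about 9 weeks, or 9.04 − (−2) = about 11 weeks. These ranges rest on a separate discrepancy: the SAP's own Trial design paragraph adds three months of follow-up to the six-week intervention, which agrees with the Protocol.

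**How many are affected.** The documents give neither the number expected to be recruited in the first eight months nor the number of focus-group attenders, so the share of answers from each visit cannot be calculated.

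**The case against.** **The mixing is conditional.** The visit tables call the form a TENS feedback questionnaire, and Protocol section 8.2 uses it for acceptability. Only the SAP ties it to blinding. The Protocol describes a direct question without naming a form, so it could be asked of everyone at Visit 4, separately from the exit form, and the tables may not be exhaustive. This stands. A reader might infer that the row is certain to be mixed, or that some participants are never asked. The documents show conflicting instructions, not either of those outcomes. Exit in the SAP can also be read to include early withdrawal.

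**Exit timing may be intended.** The SAP sentence and every visit table agree on it, and the Protocol sentence stands alone. Asking at exit would avoid drawing a continuing participant's attention to the device before Visit 5 testing. Neither document gives that reason, but the argument is fair: aligning the Protocol sentence with the SAP would also remove the conflict. It would not remove the need to split the row by visit.

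**The consequence is small.** The data are descriptive and no formal test is planned. Allocation is by permuted blocks throughout recruitment, so exit times set by recruitment date should be roughly similar across arms. This stands too. A reader might infer biased arm comparisons or a weaker treadmill-distance analysis; the documents support neither. Recall error and the influence of the focus group are possibilities, not demonstrated effects.

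**Conclusion.** The conflict over timing is plain from the text. Its consequence is conditional: if the SAP and the visit tables are followed, and participants do leave at different visits, the blinding row could combine answers from about 0 to 18 weeks after treatment, or about −2 to 18 weeks with a two-sided Visit 4 window. This assumes the Protocol's Visit 5 timing, the usual Visit 6 interval and 3 months = 13.04 weeks. On the SAP's count from randomisation the range is shorter, but that count itself needs reconciling.

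The effect is confined to one descriptive feasibility outcome. The sample size and the absolute claudication distance analysis are untouched. Severity: minor.

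**What to change.** **Preferred change.** Amend the SAP timing sentence and the Protocol's Study Schedule and Visit 4 to 6 tables to match the Protocol's end-of-treatment rule:
- Every participant completes the blinding item at Visit 4, after the treadmill test and the outcome questionnaires, and at early withdrawal where possible.
- The item is self-completed and not seen by the staff who run the Visit 5 treadmill test. The Visit 4 and Visit 5 tables show the same staff entry, so without this step the assessors could learn what participants believe about their device.
- State whether the Protocol's question is the blinding item of the TENS feedback questionnaire; if not, name the form.
- Report the item by randomised group at this single time point and label the Table 2 row accordingly. Acceptability items may stay at exit.

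**Alternative.** If exit timing is kept, correct the Protocol sentence and split the Table 2 row by exit visit.

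**Cost.** The preferred change alters Protocol tables, so it needs an amendment under Protocol section 13, plus a few minutes at Visit 4. There is a small risk of priming participants before the activPAL recording that starts at Visit 4 and before Visit 5 testing. The activPAL part of that risk already exists for those who leave at Visit 4 under the current tables.
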